13.3.3.3 Analysis of Other Variables

Analyses of blood and synovial biomarkers are summarized in Section 13.5.

The relationship of change from baseline of RAMRIS scores at Weeks 6 and 12, change in disease activity by CDAI with ACR/EULAR or CDAI remission, and change from baseline of DAS 28-ESR and ACR20-ESR response at Weeks 6 and 12 will be explored.

To assess changes in health-related quality of life, each of the remaining 7 subscales of the SF-36 item scores will be analyzed.

13.3.3.4 Sensitivity Analyses

Due to the potential bias for the synovial biopsy subjects randomized only to 200 mg group, sensitivity analyses will be performed for the primary endpoints, ACR20-CRP and DAS28-4(CRP). The sensitivity analyses will exclude synovial biopsy subjects. Similar statistical methods will be applied for these sensitivity analyses.

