- Blood samples will be collected before the first study drug dose, at 0.5 to 2 hours postdose, and at 4 to 6 hours postdose for determination of VX-509. Subjects should be restricted from food and drink intake (except water) at least 8 hours before dosing and until 2 hours after dosing (Section 11.2). Record the date and time of administration of the first dose of study drug.
- Two blood samples at least 2 hours apart will be collected for determination of VX-509 (no required relationship to dosing time). Record the date and time of administration of the most recent study drug dose before the PK sample.
- Arthroscopic synovial biopsies will only be performed in a subset of subjects at selected study sites (the Synovial Biopsy Subset). The arthroscopy at Week 4 should be obtained from the same joint as the arthroscopy performed before the first dose on Day 1 (baseline). The arthroscopic procedure at each visit will be conducted only after all other scheduled assessments are completed.
- For subjects in the Synovial Biopsy Subset only, the baseline arthroscopic procedure may be performed from Day -4 to before the first dose on Day 1.
- For subjects in the Synovial PK Subset only: In addition to the PK samples drawn for all subjects, this subset will also have a blood sample collected for determination of VX-509 (no required relationship to dosing time) immediately before the synovial biopsy and within 60 minutes before collection of the synovial fluid PK sample. Record the date and time of administration of the 2 most recent study drug doses before the PK sample.

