8 STUDY ENDPOINTS

8.1 Primary Endpoints

- Proportion of subjects who achieve ≥20% improvement in disease severity according to the American College of Rheumatology criteria (ACR20), using C-reactive protein (CRP) (ACR20-CRP) at Week 12.
- Change from baseline in Disease Activity Score 28 using CRP (4-component) (DAS28-4[CRP]) at Week 12.
- Change from baseline in Outcome Measures in Rheumatology Clinical Trials (OMERACT) Rheumatoid Arthritis Magnetic Resonance Imaging Scoring System (RAMRIS) synovitis score in designated hand (minimal assessed joints: wrist, MCP joints #2 to #5) at Week 12.
- Change from baseline in OMERACT RAMRIS bone marrow edema (osteitis) in designated hand (minimal assessed joints: wrist, MCP joints #2 to #5) at Week 12.
- Change from baseline in OMERACT RAMRIS erosion score in designated hand (minimal assessed joints: wrist, MCP joints #2 to #5) at Week 12.

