9.2 Rationale for Study Design and Study Drug Regimens

9.2.1 Study Design

The study is designed to evaluate early response to VX-509 administration, including local synovial and bone response assessment by MRI imaging and synovial biopsy (Section 6.5). The double-blind placebo-controlled design will allow comparison to variability in efficacy parameters for control subjects. No blinded joint assessor is utilized in the trial due to the small subject numbers and partial unblinding of all arthroscopy subjects, who are randomized to the 200 mg qd dose of VX-509 (Arm C) to avoid the variability inherent with doseranging. Due to the increased assay sensitivity of joint MRI, and blinded reading by 2 central readers, there is improved study power to detect RAMRIS differences and the validity of MRI data is maintained. As a sensitivity analysis, the ACR20-CRP and DAS28-4(CRP) efficacy parameters will be re-evaluated without inclusion of the arthroscopy subjects.

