11.4 Method of Assigning Subjects to Treatment Groups

Each subject will be assigned a unique screening number by the study site before evaluation of inclusion and exclusion criteria at screening. Subjects who satisfy inclusion and exclusion criteria will receive a unique subject number on Day 1, before the first dose, according to a predetermined randomization schedule.

Personnel at the study site will contact the interactive voice/web response system (IVRS/IWRS) for subject enrollment and randomized treatment assignment. The IVRS/IWRS will assign subjects at a ratio of 1:1:1:1 to 1 of the 4 treatment groups, with stratification based on previous use of any biologic response modifier drug (including anti-TNF) for RA. The subjects who additionally undergo synovial biopsy will be an exception and will only be randomized to Arm C.

The randomly assigned subject number in the IVRS/IWRS will be used to identify the individual subject for the duration of the study. Appropriate study drug will be dispensed for each subject based on the randomization information from IVRS/IWRS.

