13 STATISTICAL AND ANALYTICAL PLANS

Analysis of all data, including safety, PK profiles, efficacy, and synovial biopsies will be performed by Vertex or designee. The results of all parts of the study will be reported in the clinical study report. A detailed analysis plan for the analysis of safety data and efficacy data will be presented in a statistical analysis plan (SAP), and a detailed analysis plan for PK profiles will be presented in a clinical pharmacology analysis plan (CPAP) before the database is locked for analysis.

As synovial biopsy subjects will only be randomized to the 200 mg qd VX-509 dose (Arm C), potential bias is introduced related to patient selection, subjective assessments, and other subject interactions. To minimize the impact of this potential bias, subjects in the Synovial Biopsy Subset will know that they are not receiving placebo, but not the VX-509 dose they are receiving. Centrally blinded MRI reading limits the potential impact on RAMRIS scores.

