13.1 Sample Size and Power

Due to the small sample size of this trial, the study is not powered for demonstration of the significant changes in the treatment arm(s) as compared to placebo. Assuming that the true ACR20-CRP rates at Week 12 are 25%, 38%, 60%, and 65% for the 4 treatment groups, respectively (placebo, 100 mg, 200 mg, and 300 mg VX-509 qd), the study has approximately 25% power to demonstrate a significant difference between placebo and the 300 mg (highest) VX-509 dose.

The study will be utilized to evaluate early effects on the level of synovitis and bone marrow edema (osteitis) by MRI, and the dose-ranging information on RAMRIS scores will be utilized at end of Phase 2 to select the pivotal VX-509 dose(s) for study in Phase 3 clinical studies.

A published 24 week study evaluating golimumab 100 mg with or without concurrent methotrexate (MTX) in early RA subjects who were MTX-naïve showed mean baseline (interquartile range; minimum and maximum from any arm) RAMRIS scores of 8.8 to 10.3 (4.0 to 14.5), 8.4 to 11.5 (1.5 to 17.8), and 17.7 to 25 (8.8 to 27.0) for synovitis, bone marrow edema, and erosion, respectively. Mean (standard deviation [SD]) change from baseline in placebo arm RAMRIS scores (N = \sim 60) were 0.14 (2.98), 0.56 (3.97), and 0.24 (3.38) for synovitis, bone marrow edema, and erosion, respectively. Changes from baseline for subjects receiving golimumab 100 mg therapy alone (N = \sim 60) were -1.76 (2.76), -2.04 (5.69), and 0.51 (3.09) for synovitis, bone marrow edema, and erosion, respectively. Changes from baseline for subjects receiving golimumab 100 mg therapy with MTX (N = \sim 62) were -2.18 (3.26), -1.22 (4.88), and 0.00 (0.83) for synovitis, bone marrow edema, and erosion, respectively. Using the golimumab + MTX scores, a trial would be 80% powered with 30, 100, and 1650 subjects per arm for synovitis, bone marrow edema, and erosion RAMRIS scores, respectively.

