13.2 Analysis Sets

The Randomized Set is defined as all subjects who received a subject ID number and randomization with treatment assignment from the IVRS/IWRS.

The Full Analysis Set (FAS) is defined as all randomized subjects who received at least 1 dose of study drug. The FAS is an intention-to-treat efficacy analyses set in which subjects will be analyzed according to their randomized treatment group.

The Safety Set is defined as all randomized subjects who received at least 1 dose of study drug. The Safety Set is to be used for all safety analyses in which subjects will be analyzed according to the actual treatment they received on Day 1.

The MRI Set is defined as all subjects in the FAS Set who had at least 1 post-baseline MRI assessment.

The PK Set is defined as all subjects in the Safety Set who had at least 1 post-baseline PK sample assessment.

The Synovial Biopsy Subset is defined as all patients in the Safety Set who had at least 1 post-baseline synovial biopsy performed.

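### The analysis without biopsy subjects leaves out the three RAMRIS primary endpoints and does not say which subjects it excludes

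*Protocol*

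**What the plan says.** Section 8.1 lists five primary endpoints: ACR20-CRP, DAS28-4(CRP), and the Week 12 changes in RAMRIS synovitis, osteitis and erosion (the last worded "Change from baseline in OMERACT RAMRIS erosion score in designated hand").

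Biopsy subjects do not go through the 1:1:1:1 allocation. Section 11.4 states: "The subjects who additionally undergo synovial biopsy will be an exception and will only be randomized to Arm C". Section 9.1 expects about 6 of them, 10 at most, and plans 10 subjects for Arm C. Section 13 accepts that this may introduce bias through patient selection, subjective assessment and other interactions with subjects. On imaging it then says: "Centrally blinded MRI reading limits the potential impact on RAMRIS scores".

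The planned check is in Section 13.3.3.4: "sensitivity analyses will be performed for the primary endpoints, ACR20-CRP and DAS28-4(CRP). The sensitivity analyses will exclude synovial biopsy subjects". Section 9.2.1 announces the same check under another label: "the ACR20-CRP and DAS28-4(CRP) efficacy parameters will be re-evaluated without inclusion of the arthroscopy subjects".

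The analysis set in Section 13.2 reads: "The Synovial Biopsy Subset is defined as all patients in the Safety Set who had at least 1 post-baseline synovial biopsy performed". A footnote to Table 3-2 puts the first arthroscopy before treatment ("the baseline arthroscopic procedure may be performed from Day -4 to before the first dose on Day 1"), and the only later one scheduled is at Week 4.

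**The concern.** The RAMRIS scores are three of the five primary endpoints, and Section 13.1 assigns their dose-ranging results a role in choosing the Phase 3 dose(s). They are the primary endpoints with no check for non-random assignment to Arm C. The protocol's reason is blinded reading, which answers only one of the bias sources that Section 13 lists.

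The second issue is who is excluded. Section 13.3.3.4 points to no analysis set. The set that bears the subset's name depends on a procedure done after treatment starts. If a programmer uses it, some directly assigned subjects could remain in the analysis meant to remove them.

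**Working it through.** **1. What blinded reading and the model cover.**
- Reader bias: covered by two central readers blinded to dose and time order (Section 12.8.1).
- Baseline RAMRIS and prior anti-TNF use: covered as model covariates (Section 13.3.3.1.3).
- Recruitment at selected sites (Section 12.5): not covered.
- Assignment outside 1:1:1:1 (Section 11.4): not covered.
- Knowing that the treatment is not placebo (Section 11.10): not covered.
- A dose-modification rule that differs from that for other subjects (Section 11.3): not covered.

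**2. Reference figures.** Section 13.1 gives placebo-arm changes, mean (SD), of 0.14 (2.98), 0.56 (3.97) and 0.24 (3.38) for synovitis, bone marrow edema and erosion. For golimumab with MTX it gives -2.18 (3.26), -1.22 (4.88) and 0.00 (0.83). The differences are 2.32, 1.78 and 0.24. With SD² taken as the mean of the two variances, n per arm = 2 × SD² × (1.96 + 0.84)² / difference² gives 29, 99 and 1651. The t-based version gives 30, 100 and 1652. The protocol states 30, 100 and 1650, so its figures reproduce (two-sided 5% assumed).

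**3. Share of Arm C.** The protocol does not say whether biopsy subjects count within Arm C N = 10.
- If they do: 6/10 = 60%, up to 10/10 = 100%.
- If they sit outside the 1:1:1:1 list within 40 in total: with 6, (40 - 6)/4 = 8.5 per arm, Arm C = 14.5, share 6/14.5 = 41%. With 10, 7.5 per arm, Arm C = 17.5, share 10/17.5 = 57%.

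**4. Illustrative shift.** Shift in the Arm C mean = share × difference in expected change between biopsy and randomized subjects. The protocol gives no such difference, so 1 to 2 points is an assumption.
- Share 60%: 0.6 to 1.2 points.
- Share 41%: 0.41 to 0.83 points.
- Share 57%: 0.57 to 1.14 points.

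The reference synovitis difference is 2.32.

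**5. Precision of the proposed analysis.** Half-width = 1.96 × √(SD_placebo²/10 + SD_C²/n_C), unadjusted, with the SDs above and biopsy subjects within N = 10:

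| Score | n_C = 10 | n_C = 4 |
|---|---|---|
| Synovitis | 2.74 | 3.69 |
| Bone marrow edema | 3.90 | 5.38 |
| Erosion | 2.16 | 2.25 |

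With 10 biopsy subjects, n_C = 0 and nothing can be estimated.

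**6. Chance that a directly assigned subject stays in, if the Section 13.2 set is used.** This is 1 - (1 - q)^m, where m is the number of biopsy subjects and q the chance that one of them misses the Week 4 biopsy. The protocol gives no q. For q = 5%, 10% and 20% the result is 26%, 47% and 74% with m = 6, and 40%, 65% and 89% with m = 10.

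**The case against.** The strongest reply is that the omission is deliberate and reasoned. Readers are blinded and baseline RAMRIS is a covariate. The extra synovitis criterion for biopsy subjects (Section 10.1, criterion 9) concerns a knee or the wrist of the hand that is not scanned, while every subject meets the same criterion in the scanned hand. All of this stands and narrows the concern: the extra criterion does not select directly on the scored joints. It leaves the uncovered sources in step 1.

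On the set definition, a reader might infer that Section 13.2 is the only description of the subset, so that a subject who misses Week 4 would certainly be kept. The protocol does not support that. Sections 9.1, 9.2.1 and 11.4 describe these subjects by procedure or assignment, and Section 13.3.3.4 does not cite Section 13.2. Retention is possible, not certain. For RAMRIS the gap is narrower still: a subject who stops before 3 weeks has no repeat MRI (Section 9.1.4), and without a post-baseline scan falls outside the MRI Set.

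The last reply is that four remaining subjects settle nothing. A half-width of 3.69 can neither confirm nor rule out a 1.2-point shift. That is true, but the two planned analyses lose the same Arm C subjects, so it is no reason to omit RAMRIS alone.

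**Conclusion.** The concern holds in limited form. Section 13.3.3.4 gives no check for non-random assignment on the three RAMRIS primary endpoints, and the stated reason does not answer the selection bias that Section 13 names. The wording of the exclusion is open, and one available reading could keep directly assigned subjects in.

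The size of the bias is not known. The 0.6 to 1.2 points rest on an assumed 1- to 2-point difference and a 60% share, which requires that biopsy subjects count within Arm C N = 10. The 2.32-point yardstick comes from a 24-week study in MTX-naïve early RA.

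A reader might go further and take the Arm C RAMRIS results as shown to be biased, or RAMRIS as the sole basis for dose selection. Neither follows. No figure in the protocol shows a difference between biopsy and other subjects. Section 6.5 says MRI will help in selecting doses, and Section 13.3.4.7 refers to efficacy and MRI data together. Nor is a RAMRIS trend test missing from the check, because Section 13.3.3.1.3 specifies none.

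**What to change.** - Extend Section 13.3.3.4, and the matching sentence in Section 9.2.1, to the Week 12 change in RAMRIS synovitis, osteitis and erosion, using the Section 13.3.3.1.3 model.
- Define the excluded subjects as all those assigned to Arm C through the biopsy route in the IVRS/IWRS, whether or not a biopsy was done. Use this definition for ACR20-CRP and DAS28-4(CRP) too.
- Keep the Section 13.2 post-baseline-biopsy set for the tissue analyses only.
- State whether biopsy subjects count within Arm C N = 10, and label the results supportive. If they count within it, 4 Arm C subjects remain with 6 biopsied and none with 10, in which case the Arm C comparison cannot be made.

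The cost is a few sentences and three more tables. No new data are needed, and sample size and power do not change.

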13.3.4 Safety Analysis

The primary safety objective of the study is to evaluate the safety and tolerability of multiple doses of VX-509 when administered for 12 weeks in subjects with active RA on stable DMARD therapy. All safety analyses will be based on the Safety Set. All safety data will be presented in subject data listings.

Safety and tolerability are part of the primary objectives of this study. Safety variables include (1) adverse events; (2) labs (biochemistry, hematology, fasting lipids); (3) ECG measurements; and (4) vital signs. Safety analyses will be based on the Safety Set.

For safety variables, baseline value will be the last non-missing measurement before the first dose of study drug.

13.3.4.1 Adverse Events

Adverse events will be coded according to the Medical Dictionary for Regulatory Activities (MedDRA, Version 15.0 or higher). The number and percentage of subjects experiencing an adverse event will be summarized by the MedDRA system organ class and preferred term, as well as by treatment group. Adverse events will be classified as pre-treatment or treatment-emergent. Pre-treatment AEs will be defined as AEs that developed or worsened after informed consent up to the first dose of study drug. Treatment-emergent AEs (TEAEs) will be defined as AEs that developed or worsened at or after the first dose of study drug up to and including the Safety Follow-up Visit or 28 days after the last dose of study drug, whichever is later.

Adverse event overall summary tables will be presented for TEAEs only and will include the following:

- TEAE/ related TEAE
- TEAE leading to death/related TEAE leading to death
- Serious TEAE/related serious TEAE

- TEAE leading to treatment interruption/related TEAE leading to treatment interruption
- TEAE leading to treatment discontinuation/related TEAE leading to treatment discontinuation
- Severe/life threatening TEAEs.

The TEAE by severity summary will be presented by MedDRA system organ class and preferred term using frequency counts and percentages.

Some rules that will apply to the summarization of adverse events are:

- a subject with multiple occurrences of the same adverse event or a continuing adverse event will only be counted once
- only the maximum severity level will be presented in the severity summary
- only the aggregate of possibly related or related relationship levels will be presented in the relationship summary

Adverse events will be listed separately for those leading to death, serious SAEs, dose interruption, and permanent discontinuation.

Adverse events leading to death, SAEs, dose interruption, and permanent discontinuation will be listed separately. All adverse events through the Safety Follow-up Visit will be listed in an individual subject data listing, including pretreatment adverse events.

13.3.4.2 Clinical Laboratory

All statistical analyses of laboratory values will be performed using SI units for hematology, serum chemistry, iron studies/erythropoietin, and fasting lipid profile tests. Laboratory results in both SI and conventional units will be presented in subject data listings.

Statistical summaries of all laboratory values will be presented by treatment group at each assessment time point for each continuous chemistry, hematology, iron studies/erythropoietin and fasting lipid profile laboratory measurement. Changes from baseline will also be summarized by visit and treatment group. The number and percentage of subjects with shift changes from baseline, based on the laboratory normal ranges and the National Cancer Institute Common Terminology Criteria for Adverse Events (CTCAE) toxicity grading scale, will be tabulated for continuous laboratory assessments.

Two subject data listings of lab toxicity values of Grade 3 or higher will be provided: one listing displaying all clinically significant laboratory tests listed for subjects with any lab toxicity values of Grade 3 or higher, and the other listing with laboratory tests listed for subjects with Grade 3 or higher toxicity for the lab tests.

Change from baseline plots will be presented by treatment group and scheduled visit for selected laboratory values. The selected tests are lymphocytes, neutrophils, hemoglobin, erythropoietin, AST, ALT, creatinine, CRP, LDL, HDL, LDL/HDL ratio, triglycerides, platelet count, and each of the lymphocyte subsets.

Urinalysis and coagulation results will not be summarized in tables but only listed in subject data listings.

Clinically significant abnormal laboratory findings will be reported as adverse events.

13.3.4.3 Electrocardiograms

A summary of raw values and change from baseline values will be provided by treatment group at each scheduled visit for the following ECG measurements: PR, QT, QRS, and QTc intervals and heart rate. In addition, the number and percentage of subjects by maximum on-treatment value of QT/QTc intervals, categorized as \leq 450 msec, \geq 450 msec and \leq 480 msec, \geq 480 msec and \leq 500 msec, and \geq 500 msec, as well as maximum on-treatment change from baseline value of QT/QTc intervals, categorized as \leq 30 msec, \geq 30 msec and \leq 60 msec, and \geq 60 msec. A listing of subjects with abnormal, clinically significant ECGs will also be provided.

13.3.4.4 **Vital Signs**

The following vital signs will be summarized by treatment group at each scheduled time point: systolic and diastolic blood pressure (mmHg), body temperature, pulse rate (beats per minute [bpm]), and respiratory rate (breaths per minute). Clinically significant abnormal findings in vital signs will be reported as adverse events.

13.3.4.5 Physical Examination

Physical examination results will be presented in individual subject data listings only. Clinically relevant results will be reported as adverse events.

13.3.4.6 Other Safety Analysis

Fasting Lipid Profile

Fasting lipid profile raw values and change from baseline for total cholesterol, LDL, HDL, LDL/HDL ratio, triglycerides, leptin and lipoprotein (a) will be summarized by treatment group at each scheduled visit using descriptive statistics. Normal ranges for these tests will be presented.

Dyslipidemia Adverse Events

All subjects with treatment-emergent adverse events related to lipid abnormalities characterized by the specific Custom MedDRA Query 'dyslipidemia,' which pools the relevant ATC codes, will be summarized.

